8.1 Data Collection Methods

Where possible, participants will complete questionnaires electronically, Data will be entered directly into a secure anonymised electronic online database. For home visits and in the event of a network failure the questionnaire data will be collected on paper and entered into the online database by a member of research staff at a later time point. Only the study ID will be recorded onto the paper copy, with no identifiable information. This will be via a UoM approved system (either be UoM Qualtrics or REDCap).

Skin test and Lung Function data will be collected on paper or printed from the respective device and entered into the online database by a member of research staff at the end of the visit. Blood results will be copied from the MFT electronic patient record (Hive) into the online database. Validation of the data will be carried out during the study by members of the research team (e.g. via appropriate range and consistency checks).

8.2 Data Management

The University of Manchester is the data controller for the project

A Data Information Governance Risk review and an IG checklist has been conducted within the University of Manchester to facilitate the assessment of risks associated with processing participant data in this study. GDPR requirements and the DPIA will be reviewed annually.

A copy of relevant lung function and skin test results will be sent to the GP with a copy to the participant

8.3 Data Protection and Security

Each subject will be issued a unique identity number (UID) which will be used on all data (but not the consent form which will contain only the name). This pseudonymisation key will be generated by the data manager for the study team. The key linking the UID to the subject will be stored securely but separate to the clinical research data. Researchers from outside the University of Manchester will not have access to the key. The clinical research data will be stored under the UID and not the participant's name

Paper-based files will be kept in a locked filling cabinet in a locked office that requires staff swipe card access to the building and the room. Consent forms which contain the name of the participant (but not the UID in line with University of Manchester policy) will be stored separately from other paper documents (which will be labelled with the UID, but not the name). Computerised data will be stored on University of Manchester secure servers and will be password protected and within locked offices. Access is restricted to study team members.

Research data will be stored on a password protected database (either UoM Qualtrics or REDCap) with limited access only by study personnel. The data from the outdoor air quality questionnaire (Previous Addresses and School Details) will be stored on a separate password protected database (either UoM Qualtrics or REDCap) to the other questionnaire data. For those who consent to be contacted about future research, contact details with personal data will be stored separately on a password protected database in the secure Research Data Storage (RDS) at University of Manchester. Backups of the data will occur by the University IT support, in line with University policies.

Biological samples will be coded with the UID and barcoded locations of the samples will be recorded prior to storage, in a secure room with limited access.

In line with university record retention policy, consent forms for this study (non-interventional low risk studies) will be retained until 2 years after the end of the study. As the study will then be adopted by the Research Tissue Bank, consent forms will be passed to the research tissue bank at this time; the study data will be transferred in encrypted Excel files to the ManARTS Biobank trust servers using ZendTo.

Archiving – After the study ends, data will be archived in line with University of Manchester SOPs. Digital and hard copy data will be archived with Iron Mountain off site storage.

9) STATISTICAL CONSIDERATIONS

9.1 Statistical Analysis

We will use linear or logistic regression models to assess the associations between parameters, reporting odds ratios (ORs) with 95% confidence intervals (CIs), with Bonferroni correction. We will use latent profile modelling to derive trajectory classes based on the development of outcomes over time. We will use weighted multinomial logistic regression models to ascertain early-life risk factors associated with each clinical trajectory. The posterior probability of

membership for each trajectory class will be used as weights to reflect uncertainty of class assignment; results will be reported as relative risk ratios (RRR) with 95% CIs.

Analysis of data will be completed using appropriate statistical packages e.g. SPSS, STATA, R, unix and python. Where appropriate statistical advice will be sought from collaborators at the University of Manchester and other collaborating institutions

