5.2 Study Intervention and/or Procedures

This is an observational study. The study will comprise a single visit lasting approximately 2 hours. As this is a birth cohort study, all participants have attended previous visits and completed all these types of tests previously. During the visit the study participants will complete questionnaires, lung function tests, skin prick tests and have blood taken. In order to take part in the study, it is necessary to complete the questionnaires. All other tests are optional, as stated in the Patient Information Sheet and the Consent Form.

Participants will be asked to follow these instructions, where possible: If you are on inhalers, you will be asked not to take your inhalers for 4 hours before the test, or 12 hours if you

use long-acting inhalers, if possible. You will also need to **refrain from using antihistamines for 72 hours**, if possible. We ask that you do not eat or drink anything (except plain water) for two hours before your visit

All tests described below will be offered to those attending for a Clinic Visit. Results will be entered directly into the electronic Case Report Form which will be constructed in a University of Manchester approved software (Qualtrics or REDCap), and contain the fields outlined below. Where tests are also offered for Home Visits (HV) or Online Visit (OV) these are marked (HV) or (OV) accordingly. Tests include:

- Height, weight and body composition; blood pressure, heart rate and pulse oximetry.
 (HV)
- 2. Skin prick testing to a panel of inhalant and food allergens (including house dust mite, cat, dog, grass, trees, mould, milk, egg, peanut, hazelnut, walnut, Brazil nut, cashew and peach). (HV, inhalant allergens only)
- 3. Lung function
 - **a.** Fractional Exhaled nitric oxide (FeNO)- a non-invasive method of evaluating airway inflammation. (HV)
 - b. Airways Oscillometry Airways resistance and reactance will be measured using the THORASYS tremoFlo® or similar, in accordance with department SOP. In brief, participants will be seated with their head in the neutral position. Wearing a nose-clip, participants will be instructed to firmly hold their cheeks, as to minimize the upper airway shunt artefact, and breathe tidally through the device. Measurements consist of 16 seconds recordings and the procedure will be repeated in triplicate.

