 - c. Airway resistance and static lung volumes will be measured pre and post bronchodilator, using whole body plethysmography, to assess airway calibre, total lung capacity and air trapping. This is a highly sensitive and accurate method of measuring lung function and provides essential diagnostic information. We have previously performed these tests at age 13-16 years.
 - d. Spirometry and bronchodilator reversibility (HV): Spirometry enables us to measure the volume and flow generated by a forced expiration and has been done at each visit since age 5 years. Flow measurements as they relate to lung volume give an indication of any flow limitation in the small airways. Measurement of spirometry before and after the administration of a bronchodilator (400µg salbutamol via a metered dose inhaler and large volume spacer) is the most commonly used test for the diagnosis and monitoring of lung disease. Where possible, participants who do not want to attend clinic and are too far away for a home visit (see below) will be offered the opportunity to perform home spirometry following video training on the technique, with a spirometer that will be posted to the participant (subject to equipment being available). (OV)
- Questionnaires regarding current and previous asthma and allergy symptoms, exacerbations, medications, hospital admissions and diagnoses will be asked. (HV and OV)
 - a. Respiratory Questionnaire, based on the European Community Respiratory Health Survey Questionnaire (ECRHS), with additional questions from

International study of Asthma and Allergies in childhood (ISAAC) for continuity, and previous asthma exacerbations and prescriptions, where participants will be asked to check on the NHS app where possible.

- b. Health Survey—SF-12.
- c. food allergy questionnaire (based on the EUROPREVALL questionnaire).
- d. Asthma Control Test (ACT).
- e. Adult ADHD self-report Scale (ASRS).
- 5. Outdoor Environment and Pollution Monitoring questionnaire (previously administered at age 10-12 years; a short questionnaire about where participants lived and went to school during childhood, so that we can model exposure to pollutants and the effects on lung function and asthma). (HV and OV)

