Participants will also be free to withdraw from the study at any time without giving reasons and without prejudicing their further treatment, as participation in the research is voluntary, without their care or legal rights being affected. Data and samples already collected will be retained in the study.

7) OUTCOME MEASURES

The primary outcome will be the prevalence of asthma in the cohort, as defined by responses to the respiratory questionnaire. This will be related to other clinical outcome measures and measures of environmental exposures, biomarkers and genetic markers

The secondary outcome measures will include:

- prevalence of eczema, hay fever and food allergy as defined by questionnaires
- 2. prevalence of allergy to inhalant allergens (dust mite cat and dog and pollen) and to foods
- 3. classes of trajectories of measures of lung function (to identify predictors)
- 4. classes of wheezing illness defined by frequency of episodes and exacerbations
- 5. measurement of CC16 in relation to asthma and lung function outcomes
- 6. classes of exposure to outdoor air pollutants to relate to clinical outcomes.

8) DATA COLLECTION, SOURCE DATA AND CONFIDENTIALITY

Only data that is essential for the purposes of the study will be collected.

All members of the research team who handle the data will be appropriately trained and familiar with the policies governing the confidentiality and security of the data collected during the study.

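### Section 9.1 fixes single-step Bonferroni for the regression tests; Holm's step-down procedure gives the same familywise error control and is never less powerful, so switching is a small, free gain.

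*Protocol*

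**What the plan says.** Protocol section 9.1 opens its analysis plan with "We will use linear or logistic regression models to assess the associations between parameters", and in the same sentence commits to "reporting odds ratios (ORs) with 95% confidence intervals (CIs), with Bonferroni correction". No other multiplicity method is named.

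The sentence gives no number of tests, no family and no familywise level; a two-sided 5% level is implied by the 95% intervals. The trajectory analyses (latent profile classes, then weighted multinomial regression reporting relative risk ratios) come in later sentences of 9.1, to which the Bonferroni phrase is not attached.

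Section 9.2 explains that only people born into the cohort can take part and expects about 500. It justifies that number by the precision of a prevalence and makes no power claim.

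**The concern.** Bonferroni compares every p-value in a family of m tests with 0.05/m. Once some hypotheses have been rejected, that threshold is stricter than it needs to be for the rest. Holm's procedure relaxes it step by step and needs no further assumption to keep the familywise error at 5%.

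Because the cohort is closed, power lost to the correction cannot be bought back by recruiting more people. The stake is small: a few real associations per hundred that Holm would declare and Bonferroni would not.

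**Working it through.** **Inputs**
- From the protocol: Bonferroni as the method; a two-sided 5% level, implied by the 95% intervals (both 9.1).
- Assumed, because the protocol gives none of them: m = 14 tests in a family; 3 or 7 real effects, each with mean z = 3; equal correlation between test statistics of 0, 0.3, 0.6 or 0.8.

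The protocol states no familywise error or power for these tests, so there is no figure of its own to reproduce.

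**Step 1. Holm rejects whatever Bonferroni rejects.** Order the p-values p(1) ≤ … ≤ p(m). Holm rejects p(j) if p(i) ≤ α/(m − i + 1) for every i up to j. If p(j) ≤ α/m, each p(i) with i ≤ j is also at most α/m, which is at most α/(m − i + 1). So p(j) is rejected by Holm too.

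**Step 2. Holm holds the same error rate under any dependence.** With m0 true nulls, the first false rejection comes no later than step m − m0 + 1, where the threshold is at most α/m0. The chance that any of the m0 null p-values falls below α/m0 is at most m0 × α/m0 = α. No correlation enters the argument.

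**Step 3. Power per true effect under Bonferroni.** Level 0.05/14 = 0.00357, two-sided critical value 2.914. Power = Φ(3 − 2.914) = Φ(0.086) = 53.4%.

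**Step 4. Roughly how far Holm can go.**
- 3 real effects: the third real effect is tested at 0.05/12 = 0.00417, critical value 2.865, and Φ(0.135) = 55.4%.
- 7 real effects: the seventh is tested at 0.05/8 = 0.00625, critical value 2.734, and Φ(0.266) = 60.5%.

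Holm's average must lie between 53.4% and about these values.

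**Step 5. Simulation (200,000 draws per row, m = 14).** Familywise error is the chance of at least one rejection among the true nulls.

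| Real effects | Correlation | Power, Bonferroni | Power, Holm | Familywise error, Bonferroni | Familywise error, Holm |
|---|---|---|---|---|---|
| 3 | 0 | 53.4% | 54.5% | 3.9% | 4.3% |
| 3 | 0.3 | 53.5% | 54.5% | 3.6% | 4.1% |
| 3 | 0.6 | 53.5% | 54.5% | 2.7% | 3.0% |
| 3 | 0.8 | 53.3% | 54.3% | 1.8% | 2.0% |
| 7 | 0 | 53.4% | 57.0% | 2.5% | 3.5% |
| 7 | 0.3 | 53.5% | 57.0% | 2.3% | 3.4% |
| 7 | 0.6 | 53.4% | 56.7% | 2.0% | 2.8% |
| 7 | 0.8 | 53.3% | 56.6% | 1.4% | 2.0% |

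Holm gains about 1 point with 3 real effects and 3 to 4 points with 7, and hardly depends on the correlation. Its familywise error stays below 5% in every row. In no draw did Bonferroni reject a hypothesis that Holm kept.

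**The case against.** **Bonferroni is valid, simple and a legitimate choice.** It holds familywise error at or below nominal under any dependence, and no power claim in the protocol rests on it. This stands, and it is why the point is an improvement and not an error. It does not favour Bonferroni over Holm for testing, because Holm has the same validity on the same terms.

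**Section 9.1 reports intervals, and Holm has no simple matching ones.** This also stands. Adjusted intervals can remain Bonferroni-based. The price is that an association may occasionally be significant by Holm while its Bonferroni interval still includes the null.

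**Bonferroni can be applied piecemeal; some data will come late.** Section 11 says CC16 may be measured later on stored samples. Holm does need all p-values of a family to finish its ordering. But a rejection already made at the Bonferroni level is never reversed by Holm, so nothing is lost by waiting.

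**A stronger reading.** A reader might infer that Bonferroni will be applied to families of strongly correlated tests, such as one per allergen ("including house dust mite, cat, dog, grass, trees, mould, milk, egg, peanut, hazelnut, walnut, Brazil nut, cashew and peach") or one per lung-function index ("Airway resistance and static lung volumes will be measured pre and post bronchodilator, using whole body plethysmography"), so that the true familywise error is well under 5% and a correlation-aware method is called for. The protocol does not support this:
- Those lists in section 5.2 are measurements. Section 7 states coarser outcomes: one questionnaire-defined asthma outcome as primary, "prevalence of allergy to inhalant allergens (dust mite cat and dog and pollen) and to foods", and trajectory classes for lung function.
- No correlation is given. With 14 tests, all null, familywise error under Bonferroni is 4.9% at correlation 0, 4.5% at 0.3, 3.7% at 0.5, 2.7% at 0.7 and 2.1% at 0.8. It falls to about half of nominal only near 0.7.
- Step-down max-T (Westfall-Young) would gain more where correlation is high: with 3 of 14 effects real, about 60-61% power at correlation 0.6 and 67% at 0.8, but only 56% at 0.3. It needs joint resampling of the whole family. Here every test except the questionnaires is optional and home visits omit the food allergens, so that is a trade-off and not a free gain.

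**Conclusion.** The point holds as a minor, free improvement. For hypothesis tests, single-step Bonferroni is uniformly dominated by Holm: the same familywise guarantee under any dependence, and every Bonferroni rejection retained. That conclusion rests on no assumption about the data.

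The size does rest on assumptions: 14 tests in a family, 3 to 7 real effects, each at z = 3. On those, the gain is about 1 to 4 percentage points of power per true effect. If no effect is real there is no power to gain.

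Nothing in section 9.1 is invalid. The protocol does not establish that the actual familywise error is far below 5%. That the families and the number of tests are undefined is not counted against it, since a statistical analysis plan commonly settles them.

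**What to change.** In section 9.1, replace the Bonferroni phrase with wording such as: with Holm's step-down correction for hypothesis tests within each family; multiplicity-adjusted confidence intervals, where given, use the Bonferroni level.

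Step-down max-T may be mentioned as an option for a family whose tests prove highly correlated and whose participants have largely complete data. It should not be the default.

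The cost is one phrase. Holm needs only the p-values that Bonferroni already uses. Reports should state that test decisions follow Holm, so that the occasional mismatch with a Bonferroni interval is not misread.

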Participant and Public Involvement: Within the Manchester Asthma and Allergy Study, we have worked closely with NIHR Manchester BRC patient and public involvement and engagement centre, Vocal (https://research.cmft.nhs.uk/facilities-services/vocal). A focus group of MAAS participants was held in August 2024 to gauge participant views on conducting a further review of their health and lifestyle, and on accessing data from their health records. Information from the focus groups helped us to design the protocol, participant information sheets and consent form. Specifically, focus group participants had positive memories of taking part as children and were keen to attend a further visit, but felt reimbursement of travel expenses was appropriate. They appreciated that home visits would be available as well as online visits (with the possibility of home spirometry, which was well received), but reported that would be more likley to attend when back in Manchester visiting family. They reported that an online booking system would be more convenient, and they would value a prompt within the PIS to check with family about postcodes and addresses of homes and schools from childhood for the outdoor pollution questionnaire. On discussion of accessing their primary care records to extract information on

healthcare utilisation, diagnoses and medication prescriptions, they agreed that asking them to share information via the NHS app would be a desirable option as this allowed them to control what was shared. They asked to be copied in on study results sent to GP; for those who chose to register for the MyMFT app (linking to MFT new electronic patient record) the letter will also be visible on there. They were keen to receive an updated newsletter of study results and to include links to scientific papers (as ~ 50% had jobs in science).

12) ETHICAL and REGULATORY CONSIDERATIONS

12.1 Approvals

The study protocol will be submitted to the NHS Research Ethics Committee via the IRAS process. The study will be authorised by the Health Research Authority according to the legal requirements in England.

The selection of the subjects will not start before the approval of the Ethics Committee has been obtained and the study authorised by the Health Research Authority.

The study will be conducted in accordance with the Declaration of Helsinki, with the Good Clinical Practices guidelines and following all other requirements of local laws.

- a. Substantial amendments that require review by NHS REC will not be implemented until that review is in place and other mechanisms are in place to implement at site.
- b. All correspondence with the REC will be retained.
- c. The Chief Investigator will notify the REC of the end of the study.
- d. An annual progress report (APR) will be submitted to the REC within 30 days of the anniversary date on which the favourable opinion was given, and annually until the study is declared ended.

12.2 Risks

This is an observational study with no intervention, and it takes place at a single visit.

Blood sampling is a safe procedure and is unlikely to cause any problems.

Events that may be regarded as expected complications associated with the investigations are shown in the table below.

We do not anticipate any major ethical issues with this study. All research methods employed in this study have been previously applied in both healthy volunteers and patients with asthma. All the clinical procedures performed in this study are validated.

Tests performed during Clinic visit or Home Visits will be conducted by experienced researchers. All participants will be asked if they have any drug allergies at the start of the visit in line with MFT Medicines Policy, and this will be recorded in the hospital medical record.

Procedure	Known complications	
Spirometry	Cough, breathlessness, light headedness	
Airway Resistance, lung volumes	Cough, breathlessness, light headedness	
	Tachycardia, tremor, cough, nausea, headache. This will be	
Bronchodilators (salbutamol)	dispensed from the Trust Pharmacy and Trust SOPs will be	
	followed in relation to the dispensation and provision of this to	

	participants. Participants will be provided with a copy of the medicine information leaflet if this administered.
Oscillometry	breathlessness, light headedness, cough
FeNO	breathlessness, light headedness, cough
Skin Prick Testing	Wheals, itching. If this develops, we will offer antihistamine cream, in line with clinical practice. This will be dispensed from the Trust Pharmacy and Trust SOPs will be followed in relation to the dispensation and provision of this to participants. Participants will be provided with a copy of the medicine information leaflet if this administered.
Blood testing	Minor bruising, light headedness. It is possible that a participant could faint during blood tests; should this happen, it will be managed appropriately by the research staff

13) STATEMENT OF INDEMNITY

The University of Manchester has insurance available in respect of research involving human subjects that provides cover for legal liabilities arising from its actions or those of its staff or supervised students. The University also has insurance available that provides compensation for non-negligent harm to research subjects occasioned in circumstances that are under the control of the University.

14) FUNDING AND RESOURCES

The Manchester and Allergy Study will use equipment already available in the North West Lung Research Centre, purchased with previous grants and owned by MFT. This stored in the Manchester and Allergy Study clinic and lung function rooms, and is maintained by the medical electronics department at MFT, and calibrations are completed by the research physiologist in line with study SOPs

This includes:

- a. Blood Pressure, Heart Rate and O2 Sats will be measured on a DASH 2500 Patient Monitor.
- b. Height will be measured using a stadiometer, weight and body composition with a Tanita bioelectrical impedance analyser.
- c. a Vyaire Whole Body Plethysmograph
- d. Tremoflo Airwave Oscillometry Device.

We will purchase (from the North West Lung Centre Charity grant):

- e. a NIOX VERO for the measurement of exhaled nitric oxide
- f. associated consumables such as mouthpieces and filters,
- g. FBC consumable and measurement costs
- h. Skin prick test allergen solutions and consumables
- i. Monetary gift voucher as token of appreciation for attending (£10), and parking costs/travel expenses

Subject to equipment being available, where possible, participants who do not want to attend clinic and are too far away for a home visit will be offered the opportunity to perform home spirometry following live video training on the technique, with a handheld spirometer that will be posted to the participant. We will supply packaging so that the spirometer can be returned. It will then be made available for use in other BRC supported studies.

We have salary for a part time band 7 research nurse to plan and conduct the visits (from the North West Lung Centre Charity grant.)

The study will also be supported by the Manchester National Institute for Health and Care Research (NIHR) Manchester Biomedical Research Centre (BRC).

At the end of the study, the equipment will be used in other BRC supported studies.

15) PUBLICATION POLICY

